8 CORRELATIVE/ SPECIAL STUDIES

8.1 Laboratory Correlative Studies

8.1.1 Collection of Specimen(s)

Biopsy specimens will be collected per normal institutional methods for biopsy and surgical resection procedures.

8.1.2 Handling of Specimens(s)

At the time of the baseline biopsy, endpoint biopsy, and/or resection specimen, the tissue will be handled and processed by routine tissue protocol at the pathology laboratory of the institution performing the procedure. Standard morphologic assessment of the tissue (including H&E stain) will be performed by the pathology laboratory of the institution performing the procedure with an emphasis to avoid decalcification of the tumor material, if possible.

8.1.3 Shipping of Specimen(s)

The archived biopsy or representative portions of the resection specimen, including formalin fixed paraffin embedded block and matching H&E slide, will be sent to the laboratory of [name] at the Site Performing Correlative Study (Stanford Cancer Institute) by overnight courier at room temperature. Once archived, the tissue is stable at room temperature.

8.1.4 Site(s) Performing Correlative Study

The Site Performing Correlative Study is the laboratory of [name] at the Stanford Cancer Institute at the Stanford University Medical Center. [name] laboratory will be responsible for all the correlative study tests.

8.1.5 Coding of specimens for privacy protection

The specimens will be coded at the time of receipt in the laboratory of [name]. The specimen will be given a 5-digit number with no relationship to the subjects' HIPPA data. The key for the coded specimens and the patient data will be kept by [name] in a locked office.

9 STUDY CALENDAR

	Pre-Study	Wk 1	Wk 2	Wk 3	Wk 4	Wk 5	Wk 6	Wk 7	Wk 8	Wk 9	Wk 10	Wk 11	Wk 12	Off-Study ^d
Dabrafenib		Dabrafenib will be administered twice daily as specified in Section 4 until surgical resection						FOR SUBJECTS NOT UNDERGOING SURGICAL RESECTION: dabrafenib will continue until disease progression or intolerance						
Trametinib		Trametinib will be administered daily as specified in Section 4 until surgical resection						FOR SUBJECTS NOT UNDERGOING SURGICAL RESECTION: trametinib will continue until disease progression or intolerance						
Informed consent	X													
Demographics	X													
Medical history	X													
Biopsy of tumor for correlative studies	X							X ^g						
Surgical resection for patients with resectable tumors, and tissue collection for correlative studies								X						
Concurrent meds	X	X						X ^a						
Physical exam	X			X			X			X ^a			X ^a	X
Vital signs	X			X			X			X ^a			X ^a	X
Height	X													
Weight	X													
Performance status	X													
CBC w/diff, plts	X			X			X			X ^a			X ^a	X
Serum chemistry ^b	X			X			X			X ^a			X ^a	X
EKG within 14 days of enrollment	X													
ECHO cardiogram within 1 month of enrollment	X			X									X ^f	

	Pre-Study	Wk 1	Wk 2	Wk 3	Wk 4	Wk 5	Wk 6	Wk 7	Wk 8	Wk 9	Wk 10	Wk 11	Wk 12	Off-Study ^d
Adverse event evaluation. See Section 7 for expected AEs and Section 6 for dose modification rules.	X			X			X			X ^a			X ^a	X ^a
Tumor measurements	X	Tumor measurements are repeated every 6 weeks. After Week 7, tumor measurements are repeated every 6 to 9 weeks. Documentation (radiologic) must be provided for patients removed from study for progressive disease.											X ^d	
Radiologic evaluation (CT, MRI, X-ray)	X	Tumor measurements are repeated every 6 weeks. After Week 7, tumor measurements are repeated every 6 to 9 weeks. Documentation (radiologic) must be provided for patients removed from study for progressive disease.											X ^d	
Serum Pregnancy testing within 14 days of enrollment	X													
Ophthalmologic examination. See Section 6 on guidelines for visual changes and exam source sheet in appendix	X						X ^e							

a: Only for patients continuing on dabrafenib and/ or trametinib who have not undergone surgery.
 
b: Albumin, alkaline phosphatase, total bilirubin, bicarbonate, BUN, calcium, chloride, creatinine, glucose, phosphorus, potassium, total protein, AST, ALT, sodium.
 
d: Off-study evaluation.
 
e: Ophthalmologic exams to be repeated annually.
 
f: Every 3 months while on trametinib.
 
g: For subjects not undergoing surgical resection.
														

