3. Uncontrolled hypertension (systolic blood pressure > 140 mm Hg and diastolic blood pressure of > 90 mm Hg which cannot be controlled by anti-hypertensive therapy), CHF, or other major medical illness.			
4. Prior allergic reactions attributed to compounds of similar chemical or biologic composition to dabrafenib or trametinib.			
5. Concomitant use of strong inhibitors (eg, ketoconazole, nefazodone, clarithromycin, gemfibrozil) or strong inducers (eg, rifampin, phenytoin, carbamazepine, phenobarbital, St John's wort) of CYP3A4 or CYP2C8 . For a full list of excluded drugs see Section 4.1.2 of the protocol			
6. Concomitant use of proton pump inhibitors, H2-receptor antagonists, antacids			
7. Known G6PD deficiency			
8. Pregnant or nursing patients. Women of childbearing potential must have a negative SERUM pregnancy test within 14 days of enrollment. Women of child-bearing potential must agree to use effective contraception for 14 days prior to enrollment, throughout the treatment period and for 4 to 6 months after the last dose of study treatment.			
9. EKG with QTcB (Bazett's formula) > 480 ms done within 14 days of enrollment			
10. Interstitial lung disease or pneumonitis.			
11. A history of retinal vein occlusion (RVO).			

12. Congestive heart failure NYHA Class III or worse (Marked limitation of physical activity. Comfortable at rest. Less than ordinary activity causes fatigue, palpitation, or dyspnea.)
			

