7.3 Pregnancy

Pregnancy Testing and Prevention

The need for a screening pregnancy test depends on whether a female subject is of childbearing potential or non-childbearing potential.

A female of non-childbearing potential (ie, physiologically incapable of becoming pregnant) is defined as any female who has had a hysterectomy, bilateral oophorectomy (ovariectomy), bilateral tubal ligation or tubal occlusion, or is post-menopausal.

A practical definition accepts menopause after 1 year without menses with an appropriate clinical profile, eg, age appropriate, > 45 years in the absence of hormone-replacement therapy (HRT). In questionable cases, the subject must have a follicle-stimulating hormone (FSH) value > 40 mIU/mL and an estradiol value < 40 pg/mL (< 140 pmol/L).

A female of child-bearing potential is defined as any female who does not meet the criteria of non-childbearing potential as described in the previous paragraph.

If a female subject is of childbearing potential, she must have a serum β -human chorionic gonadotropin (HCG) pregnancy test performed within 14 days prior to randomization. Subjects with a positive pregnancy test result must be excluded from the study. Subjects with a negative pregnancy test result must agree to use an effective contraception method as described below throughout study treatment and until 4 months after the last dose of study treatment.

Novartis acceptable contraceptive methods, when used consistently and in accordance with both the product label and the instructions of the physician, are as follows:

- An intrauterine device with a documented failure rate of less than 1% per year.
- Male partner sterilization prior to the female subject's entry, and this male is the sole sexual partner for that female.
- Complete abstinence from sexual intercourse for 14 days prior to enrollment, throughout study treatment, and for at least 4 months after the last dose of study treatment. Abstinence is only acceptable when in line with the preferred and usual lifestyle of the subject. Periodic abstinence (eg, calendar, ovulation, symptothermal, post-ovulation methods, etc) and withdrawal are not acceptable methods of contraception.
- Double-barrier contraception: condom and occlusive cap (diaphragm or cervical/vault caps) with a vaginal spermicidal agent (foam/gel/cream/suppository).

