Note: Hormonal-based methods (eg, oral contraceptives) are not permitted as contraception due to potential drug-drug interactions with dabrafenib.

Female subjects who are lactating must discontinue nursing prior to the first dose of study treatment and must refrain from nursing throughout the treatment period and for 4 months following the last dose of study treatment.

If a subject becomes pregnant during the treatment period of the study, the study treatments should be stopped immediately.

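### Both drugs must stop on pregnancy, but the protocol text schedules only one pregnancy test, before enrollment, and none during treatment or before a post-surgical restart

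*Combined protocol and SAP*

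**What the plan says.** Section 7.3 gives the stop rule: "If a subject becomes pregnant during the treatment period of the study, the study treatments should be stopped immediately". Section 7.2 adds that a pregnancy on treatment is reported to the drug supplier within 24 hours of the site learning of it.

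Testing appears in three places, and all describe the same pre-entry serum test:

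- Section 3.1, exclusion criterion 8: "Women of childbearing potential must have a negative SERUM pregnancy test within 14 days of enrollment".
- Section 7.3: a serum hCG test in the 14 days before entry.
- Section 9, Study Calendar: a single mark in the Pre-Study column, in the row labelled "Serum Pregnancy testing within 14 days of enrollment".

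After a negative test the protocol relies on prevention. Under exclusion criterion 8, women of childbearing potential "must agree to use effective contraception for 14 days prior to enrollment, throughout the treatment period" and for months after the last dose. Section 7.3 lists the accepted methods and adds: "Hormonal-based methods (eg, oral contraceptives) are not permitted as contraception due to potential drug-drug interactions with dabrafenib".

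Treatment can be long. Under Section 4, unresected patients stay on both drugs until progression, unacceptable toxicity or their own decision to stop. Incompletely resected patients may restart both drugs 1 to 6 weeks after surgery if five criteria are met.

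**The concern.** The stop rule and the reporting rule can act only once a pregnancy is known, and nothing scheduled after enrollment would make it known. If contraception fails, exposure to both drugs continues until the patient reports it or a clinician suspects it. The protocol does not size the fetal harm, but its immediate stop and required contraception show that it means to avoid exposure.

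The possible exposure is longest for unresected patients and for those who restart after incomplete resection. What is at stake is patient safety. The response endpoint and the two-stage design are not affected.

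**Working it through.** **1. Is a later test scheduled anywhere?** I set the calendar, its footnotes and the restart rules side by side.

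- Calendar pregnancy row: one mark, Pre-Study. Neighbouring rows keep their Wk 3, 6, 9 and 12 marks, and Sections 3.1 and 7.3 agree on a single pre-entry test, so a lost table cell is not a likely explanation.
- Footnotes a, b and d to g: none adds a repeat test.
- Chemistry panel (footnote b): "Albumin, alkaline phosphatase, total bilirubin, bicarbonate, BUN, calcium, chloride, creatinine, glucose, phosphorus, potassium, total protein, AST, ALT, sodium". There is no hCG.
- Five restart criteria in Section 4: no earlier stop for toxicity or progression, recovery from surgery, at least 1 week elapsed, evaluable residual tumor, at most 6 weeks elapsed. None is a pregnancy test.
- Wk 9 and 12 blood draws (footnote a): "Only for patients continuing on dabrafenib and/ or trametinib who have not undergone surgery". A restarted patient therefore has no scheduled on-treatment draw after surgery.
- Other contacts: physical exams and adverse-event reviews, skin exams every 2 months, echocardiograms every 3 months on trametinib, eye exams, and imaging every 6 to 9 weeks. None includes a pregnancy test.

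Count of scheduled tests: 1 before enrollment, 0 on treatment, 0 before restart, 0 during indefinite dosing.

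**2. How old is the only test?** Inputs: test 0 to 2 weeks before enrollment (3.1), surgery at week 6 to 7 and restart 1 to 6 weeks later (Section 4). The interval from enrollment to first dose is not given and is taken as zero; any delay adds to these figures.

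- At surgery: (0 to 2) + (6 to 7) = 6 to 9 weeks.
- At restart: (0 to 2) + (6 to 7) + (1 to 6) = 7 to 15 weeks.
- Unresected: no upper limit.

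**3. How many pregnancies might occur?** The enrolled total is 11 to 21 (12.3). The number of women of childbearing potential is not given; Section 2.1 says most cases are diagnosed at 30 to 60 years. Assumption: 10% to 40% of patients.

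- Women: 11 × 0.10 = 1.1 to 21 × 0.40 = 8.4.
- Failure rate: the only one in the documents is in 7.3, "An intrauterine device with a documented failure rate of less than 1% per year". Using 1% as a ceiling:
  - all stop at week 7: 1.1 × 7/52 × 0.01 = 0.0015 to 8.4 × 7/52 × 0.01 = 0.011;
  - all treated for one illustrative year: 1.1 × 0.01 = 0.011 to 8.4 × 0.01 = 0.084.

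**4. What would added tests change?** With tests at Wk 3 and 6, at Wk 9 and 12 if continuing, before restart, and at least every 9 weeks later:

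- Screening test to Wk 3: up to 2 + 3 = 5 weeks, plus any enrollment-to-dose gap, of which at most 3 weeks are on drug.
- Unresected, Wk 3 to 12: 3 weeks between tests; after that, at most 9.
- Restart: last test at most 1 week old instead of 7 to 15, then at most 9 weeks between tests.
- Resected without restart: surgery is at week 6 to 7, so a Wk 6 test can spare at most about 1 week of drug. Mainly the Wk 3 test shortens exposure.

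**The case against.** The strongest defence is that this is a design choice with substantial prevention built in: a negative serum test at entry, contraception before, during and after treatment, a list of accepted methods, hormonal methods barred, an immediate stop and prompt reporting. Clinicians see patients at Wk 3 and 6, and unoperated patients also at Wk 9 and 12. Nothing in the documents sets a testing interval. All of this stands. It limits the weight of the point but does not supply a test.

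A reader might go further in four ways that the documents do not support:

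- **That the rules conflict.** They do not. A stop rule can coexist with detection by report or suspicion.
- **That close to one pregnancy should be expected.** Reaching 8.4 × 0.10 = 0.84 needs 21 patients, 40% of childbearing potential, a full year of treatment for every one of them, and a 10% annual failure rate. The documents give no rate for methods other than the IUD. A year for everyone also sits poorly with a trial aimed mainly at non-metastatic disease and designed not to delay surgery unduly (2.3).
- **That patients are never tested in practice.** Consent pages were removed, and the medication guides and institutional procedures (Appendices A and B) are only referenced. A local preoperative test is neither required nor ruled out.
- **That every added test helps equally.** An off-study test comes after dosing ends and cannot shorten exposure.

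**Conclusion.** The point holds as a low-cost safeguard worth adding. Followed as written, the protocol text gives its immediate-stop rule no scheduled trigger during initial, resumed or indefinite dosing.

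The expected number of events is small: at most about 0.08 in the trial, on the assumptions of 10% to 40% women of childbearing potential, one year of treatment for all, and the IUD ceiling applied to every method. The case for change therefore rests on how long an on-treatment pregnancy can go untested, which is now unlimited in unresected patients. The benefit is greatest for unresected and restarted patients and modest for those resected without restart.

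Confidence is high for what the protocol text schedules. It does not extend to the material that could not be checked.

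**What to change.** For women of childbearing potential:

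1. **Restart.** Add a sixth criterion in Section 4: a negative pregnancy test within 7 days before dosing resumes.
2. **Through Wk 12.** Add hCG to the existing Wk 3 and 6 draws, and to the Wk 9 and 12 draws for those continuing.
3. **Beyond Wk 12, or after a restart.** Do a urine or serum test at each tumor-measurement visit and at least every 9 weeks. State the 9-week limit explicitly: Section 10.1.3 ties follow-up imaging to unresected patients, while the calendar row does not.

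An off-study test is optional. Its only use is to detect and report a pregnancy that began on treatment.

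**Cost.** One calendar row with a footnote, one restart criterion and one sentence in 7.3. Tests added per woman, without the optional one:

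- Resected without restart: 2.
- Unresected for an illustrative year: 4 through Wk 12, plus 40/9 to 40/6, or 4 to 6 whole visits, giving 8 to 10.
- Restarted at week 7 to 13 and followed to week 52: 2 + 1 + (39/9 to 45/6, or 4 to 7) = 7 to 10.

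Trial total: 1.1 × 2 = about 2 to 8.4 × 10 = 84. After Wk 12 or a restart no blood draw is listed, so a separate sample is needed.

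**Downside.** A false positive could cause a short hold in the continuous dosing planned up to surgery, and one at Wk 3 could count against the two-thirds completion review in 12.5. The Wk 3 test amounts to about 1 to 8 tests in the trial. A true positive has to stop under 7.3 in any case.

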If a subject misses a dose of dabrafenib, the subject may take the dose immediately if the next dose is scheduled for at least 6 hours later. If the next scheduled dose of dabrafenib is due in less than 6 hours, the subject should skip the dose and resume dabrafenib dosing at the next scheduled dose. If a subject misses a dose of trametinib, the subject may take the dose immediately if the next dose is scheduled for at least 12 hours later.

Patients whose tumors are amenable to surgical resection will continue dosing continuously for at least 6 weeks and proceed to surgery between weeks 6 and 7, without dose interruption. Patients undergoing surgical resection will continue dabrafenib and trametinib until it is necessary to take nothing by mouth in the hours preceding surgery, but **ideally the patients will be dosed with dabrafenib and trametinib within 12 hours of the surgical resection**. Patients whose tumors are grossly completely resected will not resume dabrafenib and trametinib. Patients whose tumors are not resected completely have the option to resume the dabrafenib and trametinib at the dose they were receiving immediately prior to surgery if ALL of the following criteria are met:

1. Prior to surgery the patient did not have AEs or progression which necessitated dabrafenib or trametinib cessation.
2. The patient has recovered from surgery without unexpected complication.
3. At least 1 week has passed since surgery.
4. The patient has evaluable residual tumor.
5. No more than 6 weeks has elapsed since surgery.

Patients whose disease is judged to be not amenable to resection will continue dabrafenib and trametinib indefinitely as long as there has not been tumor progression either by RECIST v1.1 or clinical progression criteria, there have not been unacceptable adverse events and the patient has not decided to discontinue for other reasons.

Clinical evaluations for protocol purposes will take place according to the schedule defined in Section 9. Dose modifications will be according to the guidelines in Section 6.

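### Calendar footnote a excludes patients who resume both drugs after incomplete resection from the Wk 9 and Wk 12 safety evaluations

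*Combined protocol and SAP*

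**What the plan says.** - **Section 9, AE row** ("Adverse event evaluation. See Section 7 for expected AEs and Section 6 for dose modification rules"): marked at Pre-Study, Wk 3 and Wk 6 without restriction, then at Wk 9, Wk 12 and Off-Study with footnote a.
- **Section 9, companion rows:** physical exam, vital signs, CBC and serum chemistry carry footnote a at Wk 9 and Wk 12, but a plain X at Off-Study.
- **Footnote a:** "Only for patients continuing on dabrafenib and/ or trametinib who have not undergone surgery".
- **Section 9, drug rows:** beyond Wk 6 they address one group only: "FOR SUBJECTS NOT UNDERGOING SURGICAL RESECTION: dabrafenib will continue until disease progression or intolerance". The trametinib row has the parallel wording.
- **Section 4.0, schedule:** "Clinical evaluations for protocol purposes will take place according to the schedule defined in Section 9". Patients with resectable tumors "proceed to surgery between weeks 6 and 7, without dose interruption".
- **Section 4.0, resumption:** "Patients whose tumors are not resected completely have the option to resume the dabrafenib and trametinib", if five criteria are all met. Two of them set the time window: "At least 1 week has passed since surgery" and "No more than 6 weeks has elapsed since surgery".
- **Section 4.2:** AE follow-up runs for 4 weeks after the last dabrafenib dose. The only stated exception is the start of another systemic anti-cancer agent.
- **Section 12.5:** the safety table summarises data collected under the Section 9 calendar.

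**The concern.** Footnote a sets two conditions: the patient is still on drug, and the patient has not had surgery. A patient who restarts after incomplete resection can meet the first but never the second. Section 4.0 therefore authorises a treatment path for which the calendar has no drug entry and whose dated safety visits it closes. The same section sends the site to that calendar for its evaluations.

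Safety is a secondary objective (Section 1.2). A site that follows the footnote to the letter would record AEs, vital signs, CBC and chemistry at Wk 9 and Wk 12 for unresected patients on drug, but not for resected patients back on the same drugs. Non-serious AEs and laboratory changes in the second group would then come to light only through unscheduled contact or the Off-Study visit, although the Section 12.5 table is built from calendar data.

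**Working it through.** The plan gives no figure on this point, so there is none to reproduce. The check applies the footnote to each cell and then counts the visits affected.

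**1. Cells carrying footnote a.** Concurrent medications 1 (Wk 7); AE, exam, vital signs, CBC and chemistry at Wk 9 and Wk 12, 5 × 2 = 10; Off-Study AE 1. Total 1 + 10 + 1 = 12. The Wk 7 medication cell falls no later than the earliest possible restart and is not counted further.

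**2. Restart window.** Assumption: surgery falls on days 42 to 49 (weeks 6 to 7). Restart is allowed 7 to 42 days after surgery, so from day 42 + 7 = 49 to day 49 + 42 = 91.

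**3. Closed visits while back on drug.** The documents do not say on which day of a named week a visit falls, so two conventions are shown.

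| Convention | Wk 9 | Wk 12 | Two visits closed | One visit closed | None closed |
|---|---|---|---|---|---|
| End of week, day 7n | 63 | 84 | restart on days 49–63 | days 64–84 | days 85–91 |
| Start of week, day 7n − 6 | 57 | 78 | restart on days 49–57 | days 58–78 | days 79–91 |

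Each closed visit holds 5 cells, so the loss is 2 × 5 = 10, 1 × 5 = 5, or 0 cells. The convention moves the cut-off days but not the maximum of two visits. The count stops at Wk 12, because the calendar has no later dated AE column for any patient.

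**4. Comparison with another footnote.** Footnote f ties the repeat echocardiogram to being on trametinib and says nothing about surgery, so it includes a patient who resumes. The calendar thus keeps the echocardiogram open to this patient while closing AE evaluation and laboratory tests.

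**5. Off-Study column.** Of the five assessments, four have a plain X and only AE carries footnote a. A cell for patients leaving the study makes little sense if limited to patients continuing on drug. Taken literally, it also removes the Off-Study AE evaluation from resected patients, whom Section 4.2 still requires to be followed for 4 weeks.

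**6. Statistical design.** The primary endpoint is response at 6 weeks, before any restricted AE or laboratory cell. The Section 12.5 triggers count accrual and completion of treatment, not AE records.

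**The case against.** The strongest reply is that the calendar is not the only source of safety data. Section 4.2 requires AE follow-up after the last dabrafenib dose. Section 7.2 requires SAE reporting to at least 30 days after treatment stops, and CRF listing of serious and non-serious AEs. Skin checks (Section 6.2.6), echocardiograms and the Off-Study exam and laboratory tests also remain. All of this stands, and it limits the point to scheduled ascertainment. It does not remove the point: those sections impose duties but supply no dated AE, CBC or chemistry assessment for a patient on resumed drug.

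A second reply is that the surgery condition is shorthand for being off drug. That may well have been the intent, but the words say otherwise and footnote f shows that exposure-based wording was available.

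A reader might go further and infer that resected patients lose every AE evaluation after Wk 6, or have no AE follow-up after surgery. The documents do not support this. The first inference depends on the Off-Study superscript, which is probably a slip. The second is contradicted by Sections 4.2 and 7.2. For resected patients who do not resume, Section 4.2 sets a follow-up duty without requiring a dated calendar visit. The lack of a Wk 9 visit for them is therefore not an inconsistency, and a wish for one would be a preference.

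**Conclusion.** The inconsistency is real and minor. As written, footnote a excludes patients who resume both drugs under Section 4.0 from up to two scheduled safety visits, or up to 10 assessment cells. A late restart loses one visit or none. The maximum assumes surgery on days 42 to 49 and an early restart; the exact cut-offs depend on a visit-day convention that the documents do not state.

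The Off-Study AE superscript is a second, probably typographical, fault in the same footnote. A slip cannot be proved from the text.

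The consequence is confined to scheduled collection of non-serious AEs and laboratory safety data on resumed drug, and so to the descriptive table in Section 12.5. The Simon boundaries, type I error, power and Section 12.5 triggers are untouched. The documents give neither the share of patients resected nor the share who resume, so the number affected cannot be estimated.

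**What to change.** Reconcile Section 9 with Sections 4.0 and 4.2:

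1. Reword footnote a and the dabrafenib and trametinib rows so that they do not exclude patients who resumed drug after surgery.
2. Check the superscript on the Off-Study AE cell and remove footnote a, so that the cell matches the exam, vital signs, CBC and chemistry rows.

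Neither change alters who may resume treatment or how.

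The cost is a calendar amendment, up to two scheduled visits' records (AE, exam, vital signs, CBC and chemistry) per patient who resumes, and one Off-Study AE record per resected patient. Sample size, type I error and power do not change.
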